8.5 Dose and Administration

Subjects will apply treatment once daily for up to 12 weeks to all active lesions identified at baseline and new lesions that arise during treatment. If the investigator determines all lesions are cleared at a clinic visit, the treatment may stop. If treatment is stopped due to clearance, subjects will continue regularly scheduled visits through Week 24/ET2.

An increase in the number of MC lesions (with or without inflammatory reaction) during the early treatment phase is often observed. It is important to instruct the subject/caregiver to treat the new lesions as well as the existing lesions.

Each dose will consist of berdazimer gel or vehicle gel with hydrogel thoroughly mixed together by the subject or caregiver and applied to the lesions and approximately 1 cm surrounding each lesion. Periocular lesions will be treated if the lesions are at least 2 cm from the edge of the eye. If a subject has more than 20 MC, a second dose of berdazimer gel or vehicle gel with hydrogel can be prepared to ensure appropriate coverage of all lesions.

At the investigator's discretion, the subject may be placed on a drug holiday for up to 2 weeks at a time in the event of a significant local skin reaction (LSR). This will be captured in the electronic data capture (EDC) system and the subject's diary. The investigator should instruct the subject how long to hold study drug and the planned date to re-start treatment. Site staff should contact the subject on the day of the planned re-start and assess whether the LSR has resolved enough to resume treatment. If it has not resolved sufficiently, the drug holiday may be extended as long as the entire extension has not exceeded 2 weeks. If the LSR flares after re-introduction of study drug, the study drug should be permanently discontinued and the EDC system updated appropriately. Please see [Section 7.2.4](#) for additional information.

8.6 Accountability

The dispensing and return of all study drug will be recorded on a dispensing log. The subject number/initials, and the initials and date of the person dispensing and receiving the returned medication will be documented on this form. All study product will be weighed at the time it is dispensed and when it is returned. The tube weights will be recorded in the electronic case report form (eCRF).

Inventory records must be readily available for inspection by the trial monitor and/or auditor, and open to government inspection at any time.

Study drug returned by subjects at will be held on site until accountability has been completed. The site will be instructed on return or destruction of used and unused clinical supplies.

8.7 Prohibited Concomitant Medication/Therapy

Any medication/therapy used by the subject following first application of study product will be considered a concomitant medication (e.g., aspirin, acetaminophen, birth control pills, vitamins, etc.). Every attempt should be made to keep concomitant medication/therapy dosing constant during the study. Any change to concomitant medications/therapies should be noted on the subject's study record and in the study database. When applicable, an AE should be completed for any subject starting a concomitant medication/therapy after enrollment into the study.

Immunosuppressive treatment is prohibited during the study. Use of topical calcineurin inhibitors or steroids on MC or within 2 cm of MC lesions is prohibited within 14 days of baseline and during the study. Use of the following concomitant medications to treat MC 14 days prior to baseline and during the study is prohibited: podophyllotoxin, imiquimod, cantharidin, sinecatechins, topical retinoids, oral or topical zinc, other homeopathic or over-the-counter products including, but not limited to, ZymaDerm and tea tree oil, cimetidine and other histamine H₂ receptor antagonists. Surgical procedures to treat MC (cryotherapy, curettage, other) are prohibited during the study.

8.8 Compliance

Subjects will be provided a diary to record doses. Review of subject compliance will be conducted at each visit and missed doses recorded on the subject diary will be recorded on the eCRF.

No reconciliation will be performed on the diary compliance against the tube weights. Subject compliance will be based on calculation from the missed doses recorded from the subject diary only.

9 ADVERSE EVENTS

Adverse events will be assessed and collected after the initiation of study drug treatment through the end of the subject's last visit. In order to avoid bias in eliciting AEs, subjects/caregivers should be asked the following non-leading question: "*How have you felt since your last visit?*" Adverse events will be assessed and reported after the subject is dosed, beginning from Baseline through the end of the subject's last visit. SAEs will be collected from the time of consent through the end of the subject's last visit. Adverse events that occur from time of consent up to the time of treatment administration should be recorded as medical history for all participants. Treatment-related

adverse events will be followed up until resolution or up to one year after last treatment, whichever occurs earlier.

9.1 Documenting Adverse Events

All AEs (serious and non-serious) reported by the subject must be recorded on the subject's study record and entered into the study database no later than 5 days of the site's first knowledge. The site must report related SAEs to the Sponsor within 24 hours after first knowledge of the event by the study site. The date of onset, date ended, accurate event term, seriousness, severity, outcome, relationship to study drug, therapy required, and action taken regarding study drug and study participation will be reported for each AE.

Significant LSRs (as judged by the investigator) and scarring (pitted scars $\geq 1\text{mm}$ in depth), scars that are larger than the original MC and/or extend outside the treatment area, and hypertrophic/keloid scars will be captured as adverse events.

9.2 Assessment of Severity

The investigator is responsible for evaluating all AEs and determining the severity of the event. Severity will be categorized according to the following definitions:

- Mild: Event may be noticeable to subject; does not influence daily activities; usually does not require intervention
- Moderate: Event may be of sufficient severity to make subject uncomfortable; performance of daily activities may be influenced; intervention may be needed
- Severe: Event may cause severe discomfort; usually interferes with daily activities; subject may not be able to continue in the study; treatment or other intervention usually needed

The investigator will follow all subjects who experience AEs as described in [Section 9.4](#).

9.3 Assessment of Causality

Relationship of each AE to study drug must be assessed.

Several factors should be considered when assessing the relationship (causality) of an event to the study drug or administration of the study drug.

- Alternative etiology – Is the event due to an underlying disease/condition being treated or to another known, underlying disease/condition of the participant?

- Known relationship – Has the event been observed before in participants treated with this product or similar products?
- Temporal relationship – Is there a reasonable temporal relationship between the time of onset for the event and the administration of the study drug?
- Concomitant medication – Is the event a known side effect of a concomitant medication?

Per the Council for International Organizations of Medical Sciences (CIOMS) VI working group, the use of “cannot-be-ruled-out” to imply drug relatedness will lead to excessive over-reporting and excess noise in the system. It is virtually impossible to completely rule out the role of a drug in causing an adverse event in single-case reporting. Differentiating from the procedural causes may also be difficult. Hence, the review of aggregated controlled data is an important component for the determination of the safety profile of any investigation product. Aggregate review is completed by the Sponsor.

Therefore, given the above, the Investigator should assess the relatedness to the study drug using a standard of a reasonable possibility of a causal relationship between the study drug and the AE, as per the examples in the table below:

Assessment of Causality	
Reasonable possibility: classification includes definitely, probably (likely), possibly related events	
 • Reasonable temporal sequence to drug administration • Event can be fully attributable to administration of the study drug • Known pharmacological action of the study drug • Specific tests available (positive allergy test, antibodies, metabolites) • As adverse drug reaction in the product information (Investigator's Brochure) • Reported in the literature as a possible side effect • Dechallenge (event abates on discontinuation of the study drug/without treatment) • Rechallenge positive (event reappears on re-exposure to study drug)

	
 Not explained otherwise by the subject's clinical state or medical history or by other concomitant agents/therapies, etc.
No reasonable possibility: classification includes definitely not, probably not, unlikely related events	
 No reasonable temporal sequence to study drug administration Event is explained by a number of other factors such as a subject's clinical state, medical history or other concomitant agents/therapies Etiology has been clarified and is in no way related to the study drug No reason for suspecting a causal relationship to the study drug and Investigators have established this beyond reasonable doubt

The causal relationship will be recorded on a binary scale by answering yes or no the following questions: is there a reasonable possibility of a causal relationship between the study drug and the AE? The phrase “reasonable causal relationship” means to convey, in general, that there are facts, evidence or argument that support a causal relationship to the study drug.

9.4 Adverse Event Follow-up

9.4.1 Follow-Up of Non-Serious Adverse Events

Non-serious AEs that are not resolved at the time of the last scheduled study visit (Week 24/ET2) must be recorded in the study database as ongoing/not recovered/not resolved. No further follow-up will occur for any AEs that are not related to the study drug unless this is required by a health authority or the Medical Monitor.

Treatment related adverse events, including LSRs, pitted scars \geq 5 mm in diameter or \geq 1mm in depth originated from MC lesion and hypertrophic scars/keloid, will be followed up until resolution or up to 1 year after last treatment, whichever is sooner.

9.4.2 Follow-Up of Post Study Serious Adverse Events

Serious adverse events that are identified on the last scheduled contact (Week 24/ET2) must be recorded in the study database and reported to the CRO according to the reporting procedures outlined in [Section 10](#). This may include unresolved previously reported SAEs, or new SAEs. The investigator should follow these SAEs until the events are resolved, or the subject is lost to follow-

up. The investigator should continue to report any significant follow-up information to the Sponsor and the IRB up to the point the event has been resolved. Resolution means the subject has returned to the baseline state of health, or the investigator does not expect any further improvement or worsening of the subject's condition.

9.5 Pregnancy

Females 9 years of age and older must use an effective method of birth control during the course of the study and for 30 days following their final study visit. The following are considered acceptable methods of birth control for this study: abstinence with a documented acceptable method of birth control if the subject becomes sexually active, oral contraceptives, contraceptive patches, contraceptive implant, vaginal contraceptive, double-barrier methods (e.g., condom and spermicide), contraceptive injection, Intrauterine Device (IUD), hormonal IUD, permanent contraception, same sex partner or partner who has had a vasectomy. Tubal ligation is not considered to be surgical sterilization; women with tubal ligations will be required to complete UPTs at the required timepoints.

A female is considered to be of childbearing potential unless she is post-menopausal (no menses for 24 consecutive months), surgically sterilized (documented hysterectomy, documented bilateral salpingectomy, documented bilateral oophorectomy) or under 9 years of age. Tubal ligation does not meet the definition of surgically sterile.

Before enrolling any subject in this clinical trial, the Investigator must review guidelines about study participation including the topics below:

- Informed consent document
- Pregnancy prevention information
- Risks to unborn child(ren)
- Any drug interactions with hormonal contraceptives
- Contraceptives in current use
- Guidelines for the follow-up of a reported pregnancy

Prior to study enrollment, all subjects must be advised of the importance of avoiding pregnancy during participation in this clinical study and the potential risk factors for an unintentional pregnancy. The subject must sign an informed consent document stating that the above-mentioned risk factors and the consequences were discussed.

During the study, females 9 years of age and older should be instructed to contact the investigator immediately if they suspect they might be pregnant (e.g., missed or late menstrual cycle). Study drug shall be held immediately if a subject is suspected to be pregnant and study drug must be permanently discontinued if pregnancy is confirmed. The Investigator must immediately notify the medical monitor/CRO of any female subject who becomes pregnant any time during study participation, record the information on the pregnancy notification form and email the form to the CRO. Subjects found to be pregnant prior to Week 12 will stop study drug treatment, continue with study visits through Week 24 and follow up with pregnancy outcome. Beyond Week 24, the site should follow-up with the subject periodically during the pregnancy for ongoing health and safety information through the end of the pregnancy, as applicable. The investigator is responsible for following the pregnancy through the end of the pregnancy and for providing the assessment of the healthy live birth or for reporting any abnormal outcome such as stillbirth, miscarriage, or deformity to the CRO/Sponsor (Note: Congenital anomaly/birth defect/ etc. are considered SAEs and require separate reporting per [Section 10](#).)

9.6 Overdose

There is no specific antidote for SB206. In the event of an overdose, best supportive care should be utilized. Methylene blue may be used to treat subjects exhibiting methemoglobinemia. The Medical Monitor/CRO/Sponsor must be notified of any subject exhibiting signs of methemoglobinemia.

10 SERIOUS ADVERSE EVENT

10.1 Definition of Serious Adverse Event

A SAE is any event that meets any of the following criteria:

- Death
- Life-threatening event (i.e., the subject was at immediate risk of death from the event as it occurred. It does not include a reaction that if it had occurred in a more serious form might have caused death. For example, drug induced hepatitis that resolved without evidence of hepatic failure would not be considered life threatening even though drug induced hepatitis can be fatal.)
- Inpatient hospitalization or prolongation of existing hospitalization (AEs requiring hospitalization should be considered SAEs. Hospitalization for elective surgery or routine clinical procedures that are not the result of AE (e.g., elective surgery for a pre-existing condition that has not worsened) need not be considered AEs or SAEs. If anything,

untoward is reported during the procedure, that occurrence must be reported as an AE, either 'serious' or 'non-serious' according to the usual criteria. In general, hospitalization signifies that the subject has been detained (usually involving at least an overnight stay) at the hospital or emergency ward for observation and/or treatment that would not have been appropriate in the physician's office or outpatient setting. When in doubt as to whether 'hospitalization' occurred or was necessary, the AE should be considered serious.)

- Persistent or significant disability/incapacity (if the experience results in a substantial and/or permanent disruption of the subject's ability to carry out normal life functions)
- Congenital anomaly/birth defect in the offspring of a subject who received SB206 or Vehicle Gel
- Other: Important medical events that may not result in death, be life-threatening, or require hospitalization, may be considered an SAE when, based upon appropriate medical judgment, they may jeopardize the subject and may require medical or surgical intervention to prevent one of the outcomes listed in this definition. Examples of such events are:
 - Intensive treatment in an emergency room or at home for allergic bronchospasm
 - Blood dyscrasias or convulsions that do not result in inpatient hospitalization
 - Development of drug dependency or drug abuse

10.2 Reporting Serious Adverse Events

Any SAE, whether deemed drug-related or not, must be reported to the CRO as soon as possible after the investigator or coordinator has become aware of its occurrence. The investigator/coordinator must notify the CRO within 24 hours of notification of the event. When appropriate, Novan will notify the appropriate regulatory body of drug related SAEs.

If a subject experiences an SAE or pregnancy, the investigator must:

1. Report the SAE or pregnancy immediately (within 24 hours) after the Investigator becomes aware of the event.
2. Complete an SAE or pregnancy notification form and send the appropriate reporting form to the safety office within 24 hours of knowledge of the event.
3. Obtain and maintain all pertinent medical records, information and medical judgments of medical personnel who assisted in subject's treatment and follow-up and document as appropriate.

4. Provide a more detailed report to both the CRO and the IRB, if applicable, no later than seven days after the Investigator discovers the event as further information becomes available, and when necessary update the information with follow-up information including outcomes. This report should include a statement as to whether the event was or was not related to the use of study drug.
5. The Investigator will notify the IRB of the SAE or pregnancy according to specific IRB requirements.
6. The Investigator will collect information on SAEs until the subject's health has returned to baseline status, until all parameters have returned to normal, or remaining health issues have otherwise been explained.
7. The Investigator is responsible for following pregnancies through the end of the pregnancy and for providing the assessment of the healthy live birth or for reporting any abnormal pregnancy outcome such as stillbirth, miscarriage, or deformity to the CRO/Sponsor.

For clarity on how to record an adverse event that progresses into a serious adverse event, there should be two events recorded: the first event would be the beginning adverse event, and the second event would be the serious adverse event (i.e. only the time the AE qualified as serious). Resolution of the SAE should be recorded in the same manner, two end dates for SAE and AE, where the SAE and AE may or may share the same end date.

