12.1.3 Analysis of Safety

12.1.3.1 Adverse Events

All AEs that occur during the study will be recorded and classified on the basis of Medical Dictionary for Regulatory Activities (MedDRA) terminology. Treatment-emergent AEs (TEAEs) are defined as AEs that occurred any time on or after the first in-clinic application of study drug through the last application of study medication. Medical history noted prior to the first study drug administration that worsen after Baseline will also be reported as AEs and included in the summaries.

Treatment-emergent AEs will be summarized by treatment group, the number of subjects reporting a TEAE, System Organ Class (SOC), preferred term, severity, relationship to study drug (causality), and seriousness. When summarizing AEs by severity and relationship, each subject will be counted only once within a system organ class or a preferred term by using the event with the highest severity and greatest relationship within each classification.

Serious AEs will be summarized by treatment group, severity, and relationship to study drug, and individual SAEs will be listed by subject. In addition, a list of subjects who prematurely discontinue from the study due to an AE will be provided.

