13.1 Adverse Events

All AE summaries will be restricted to treatment-emergent AEs (TEAEs), which are defined as those AEs that occurred any time on or after the first in-clinical application of study drug through the last application of study medication and those existing AEs that worsened during this same period. If it cannot be determined whether the AE is treatment emergent due to a partial onset date, then it will be counted as such; see [Appendix B](#) for the imputation of missing dates algorithm. Verbatim terms in the eCRFs will be mapped to preferred terms and system organ classes using the MedDRA Version 22.0.

Each AE summary will be displayed by treatment group. Summaries that are displayed by system organ classes and preferred terms will be ordered by descending order of incidence of system organ class and preferred term within each system organ class. Summaries of the following types will be presented:

- Overall summary of TEAEs that contain an overview of each item below.
- Subject incidence of TEAEs and total number of unique TEAEs by MedDRA system organ class and preferred term.
- Subject incidence of TEAEs by MedDRA system organ class, preferred term, and maximum severity. At each level of subject summarization, a subject is classified according to the maximum severity if the subject reported 1 or more events. Adverse events with missing severity will be considered severe for this summary.

- Subject incidence of TEAEs by MedDRA system organ class, preferred term, and closest relationship to study drug (Related/Not Related). Related AEs are those reported as “Definite,” “Probable,” or “Possible,” and unrelated AEs are those reported as “Unlikely” or “Unrelated.” At each level of subject summarization, a subject is classified according to the closest relationship if the subject reported 1 or more events. Adverse events with a missing relationship will be considered related for this summary.
- Subject incidence of serious TEAEs and total number of unique serious TEAEs by MedDRA system organ class and preferred term.
- Subject incidence of TEAEs leading to study drug discontinuation by MedDRA system organ class and preferred term.
- Subject incidence of TEAEs leading to death as an outcome by MedDRA system organ class and preferred term.

Separate listings of all AEs, all SAEs and all AEs leading to study drug discontinuation will be provided.

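### An AE that starts on drug and first becomes serious after the last application is missing from the by-arm serious-TEAE table (14.3.1.5), because it is split into two unlinked records

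*Combined protocol and SAP*

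**What the plan says.** **Recording.** Protocol 10.2 asks for two entries when an AE progresses to an SAE. The first is the initial AE. For the other, "the second event would be the serious adverse event (i.e. only the time the AE qualified as serious". Resolution is handled the same way, with "two end dates for SAE and AE, where the SAE and AE may or may share the same end date".

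**Tabulation.** Section 13.1 of the latest SAP says "All AE summaries will be restricted to treatment-emergent AEs (TEAEs"). The window runs from the first in-clinic application "through the last application of study medication and those existing AEs that worsened during this same period". Protocol 12.1.3.1 has the same end point: "AEs that occurred any time on or after the first in-clinic application of study drug through the last application of study medication". Neither document adds a lag after the last application.

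**Tables affected.** Table 14.3.1.5 is described as "Subject incidence of serious TEAEs and total number of unique serious TEAEs by MedDRA system organ class and preferred term". Table 14.3.1.7 is "Subject incidence of TEAEs leading to death as an outcome by MedDRA system organ class and preferred term". Table 14.3.1.2 gives subject incidence and a total of *unique* TEAEs. The SAP does not define *unique*.

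**Outside the TEAE restriction.** SAP 13.1 also plans listings of all AEs and all SAEs, Section 13 a listing of all deaths, and Section 6 a listing of subjects who need a narrative, including for an SAE or death. Protocol 12.1.3.1 describes a summary of serious AEs by treatment group, severity and relationship, with no treatment-emergent restriction. SAP 13.1 narrows this to serious TEAEs, and SAP Section 14 does not list the change.

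**The concern.** The recording rule gives the serious phase of an event its own, later start. If that start falls after the last application, the SAE record is outside the TEAE window, while the record that is inside the window is not serious. The worsening clause does not help, because it credits worsening only inside the same window.

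This is not the usual question of how to treat events that begin after treatment. Here the event began on treatment, and ordinary single-record coding would make it a serious TEAE under the existing window.

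At stake is the only by-arm table of serious events. The sequence can arise in this trial: local reactions may lead to stopping (protocol 8.5: "If the LSR flares after re-introduction of study drug, the study drug should be permanently discontinued"), treatment may end at clearance, and SAEs are collected until the last visit (protocol Section 9).

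**Working it through.** The documents state no figure for this point, so there is nothing to reproduce. The check runs one hypothetical subject through both rules. The days are illustrative assumptions.

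**Inputs.** Two records, with the SAE starting when the event becomes serious (protocol 10.2). Window from Day 1 to the last application (SAP 13.1). The comparator is a single record dated from AE onset and upgraded to serious.

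- Case A: AE onset Day 20, last application Day 25, serious from Day 28.
- Case B: AE onset Day 20, serious from Day 28, last application Day 85.

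A record is treatment-emergent if Day 1 ≤ start ≤ last application.

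| Case and rule | TEAE records | Subjects in TEAE incidence | Serious-TEAE records | Subjects in serious-TEAE table | Rows in SAE listing |
|---|---|---|---|---|---|
| A, two records | 1 | 1 | 0 | 0 | 1 |
| A, one record | 1 | 1 | 1 | 1 | 1 |
| B, two records | 2 | 1 | 1 | 1 | 1 |
| B, one record | 1 | 1 | 1 | 1 | 1 |

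**Case A.** The AE record (20 ≤ 25) is a TEAE. The SAE record (28 > 25) is not. Table 14.3.1.5 shows 0 instead of 1.

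**Case B.** Both records are TEAEs, but only one is serious, so Table 14.3.1.5 is right at 1. Subject incidence is also right. Only the event total in Table 14.3.1.2 can go from 1 to 2, and only if *unique* means one per record.

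**Length of the exposed period.** The Week 24 visit is nominally Day 169. Days from last application to that visit:

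- last application Day 85: 169 − 85 = 84
- last application Day 57: 169 − 57 = 112
- last application Day 29: 169 − 29 = 140

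**How many SAEs to expect.** Phase 2 had 0 SAEs in 256 subjects (protocol 1.1.4). The one-sided upper 95% bound is 1 − 0.05^(1/256) = 1.16%. Applied to 340 subjects, 0.0116 × 340 ≈ 4. This bounds all SAEs, pooled over vehicle and four active regimens. The events at issue are a subset and may be none.

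**The case against.** The strongest reply is that nothing is hidden. The event remains in the all-AE and all-SAE listings, in the narrative-subject listing and, if fatal, in the death listing. If drug was stopped for the original AE, that record also belongs in Table 14.3.1.6. With few SAEs, anyone reading the listings would see the case. This stands as far as it goes: the event leaves the table, not the report. But a listing does not replace a count by arm, and no planned table would restore the event.

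A second reply is that a link may exist in the annotated eCRF or the derived-dataset specifications, which the SAP mentions but which are not available here. The SAP also does not say in so many words that it classifies record by record. That is possible, but the protocol calls the two entries two events, the SAP defines treatment-emergence per AE, and neither states a link. Appendix B can default an SAE with a missing or partial onset date to treatment-emergent. It does not help where the date is known.

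A reader might infer more than the documents support:

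- **That the event always leaves the fatal-TEAE table.** Table 14.3.1.7 selects on outcome, not on the serious flag. Protocol 9.1 asks for an outcome for each AE, and 10.2 lets the records share an end date. The original record may carry the fatal outcome and stay in the table. The documents do not say which record does.
- **That an event turning serious on drug is counted twice throughout.** Case B shows otherwise: subject incidence and Table 14.3.1.5 are unaffected.
- **That reactions tend to turn serious after the last application.** The documents give no such evidence. The discontinuation rule in 8.5 concerns local reactions, not serious events. Six Phase 2 subjects stopped for application-site reactions, and there were no SAEs. If dosing resumes after a drug holiday, the last application moves later and the event can stay inside the window.

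**Conclusion.** The point holds for Table 14.3.1.5. As written, an AE that begins on drug and first becomes serious after the last application is shown as a non-serious TEAE, and the by-arm serious-TEAE table omits it. The error is one subject and one event per occurrence. The number of occurrences is unknown and may be zero. With SAEs this rare, one occurrence could empty the table.

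Two secondary effects are conditional. The event is also absent from Table 14.3.1.7 if only the SAE record carries the fatal outcome. The event total in Table 14.3.1.2 rises by one for an event that turns serious on drug, if *unique* means per record.

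The conclusion assumes that treatment-emergence is assigned to each record from its own start date, that the SAE start date is known, and that no unseen specification links the records. It does not touch the efficacy analysis.

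**What to change.** In SAP 13.1:

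- Link the initial AE and its SAE record by an identifier.
- Assign treatment-emergent status to linked records from the onset of the originating AE.
- Carry forward the worst seriousness and outcome across the pair, which also settles where a fatal outcome is counted.
- Define *unique* so that a linked pair counts as one event.

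In addition, add a by-arm summary of all SAEs through Week 24, as protocol 12.1.3.1 states without a treatment-emergent restriction, or declare the narrowing to serious TEAEs in SAP Section 14. The extra table would also bring the event back into a comparison by arm without changing protocol 10.2.

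The cost is one linking field or derivation rule and one more table. Subjects are not affected. The rule should be fixed before the Week 12 data are unblinded.
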